### **3.6. Description of Baseline Data**

Demographic details (e.g., age, sex, race, ethnicity, military service), medical history (e.g., co-morbidities), and baseline labs will be evaluated overall, and by intervention group.

### **3.7. Safety Data**

The safety information to be collected for this study include the description of the event, distinction between serious and non-serious adverse event, severity and expectedness of the event, relatedness to the study intervention, and outcome of the event. In addition, data on all events will be classified using the Medical Dictionary for Regulatory Activities (MedDRA) (Version 9.0) coding dictionary.

Related AE data will be collected for all consented subjects from the time of consent until the end of participation in the study. If a patient receives care at a non-VA facility for an adverse event they experience, research personnel will obtain the requisite release of information form(s) from the patient and once received, acquire the pertinent medical records from the facility.

SAE reporting will start at the time of patient consent and continue until 30 days after the patient's involvement in the study.

For reporting to the DMC and inclusion in the final report safety data will be aggregated for the sample as described in **3.3**. Data will be summarized as follows.

- Frequency and percentages of all non-serious and serious adverse events overall and by intervention group
- Frequency and percentages of all unique subjects with non-serious and serious adverse events overall and by intervention group
- Rates of non-serious and serious adverse events overall, by intervention group, and by center, calculated as # events/ person-time in years
- Tabulation of event type, MEDRA classification, severity, expectedness, relatedness and outcome of all events overall and by intervention group

## **4. Sample Size and Power**

The results for the primary hypothesis will be analyzed by using a one-sided 95% confidence interval on the difference in proportion of participants with one or more gout flare events during phase 3. The test of the difference between proportions will have one-sided type I error of 5%.

Starting with a total of 950 participants and allowing up to 10% dropout, the test has 90% power to reject the null hypothesis of inferiority with a total of 850 participants, 425 participants per treatment arm.

Sample recruitment and subsequent event rates will be summarized and presented to the DMC bi-annually. These reports will be used for monitoring the progress of the study and any modification to the recruitment schedule or the statistical analysis plan will be at the recommendation of the DMC.

## **5. Statistical Methods**

### **5.1. Handling of Missing Data in Analysis**

During phase 3, 2% of subjects have been estimated to drop out. This is less than the dropout rate in phase 1 and 2 because no one is having dose titration. For purpose of making the power calculation conservative, the rate of attrition has been estimated as being up to 10%, and sample size has been adjusted accordingly to maintain 90% statistical power for the primary analysis.

The high dropout rate reflects clinical practice and not the more vigilant patient monitoring in a clinical trial. Distribution of participants lost to follow-up and missing data on key variables across the treatment groups will be monitored throughout the study. Missing primary endpoint data will not be imputed. All those with missing endpoint data either due to attrition or active withdrawal of consent will be excluded from primary analysis. Missing covariate data will be imputed in selected circumstances as described in [3]. We will explore the possibility of non-random dropout on endpoint data [4].

### **5.2. Balancing During Randomization**

Simple randomization will be used to ensure that equal proportions of participants with the following characteristics are in the two treatment arms:

- 1) CKD Stage 3;
- 2) marked hyperuricemia defined as a sUA  $\geq$  9.0 mg/dl;
- 3) presence of tophi (focused examination involving the hands, elbows, feet, and ears, which are the most common sites for tophaceous deposits); and
- 4) participants with current receipt of allopurinol.

Furthermore, to guarantee enrollment of a sufficient number of gout participants with CKD stage 3 (eGFR  $\geq 30$  but  $< 60$  ml/min/1.73 m^2) to address a key secondary objective (see Section 2), we will randomize at least one participant with CKD Stage 3 for every two participants with preserved renal function (eGFR  $\geq 60$  ml/min/1.73 m^2).

Distribution of all these variables across the treatment groups will be closely monitored throughout the study. If any unbalancing happens on one or more characteristics listed above, a biased coin algorithm will be implemented to remedy the condition.

### 5.3. Univariate and Bivariate Distributions of Baseline, Safety and Follow-up data

- In general, the number of observations, mean, median, standard deviation, minimum, and maximum will be calculated for continuous variables. The number of decimal places will be two decimal places.
- Frequencies and percentages will be calculated for categorical data.
- Distribution of continuous variables and proportions of categorical variables will be tabulated by intervention group, and t-test and chi-square tests will be performed to evaluate if these variables are balanced between 2 intervention groups.
- For the primary analysis, baseline is defined as the starting date of Phase 3.

### 5.4. Primary Efficacy Analysis

Primary efficacy analysis will include patients who remain on study when phase 3 begins.

The primary outcome is the difference (D) in proportion of patients with one or more gout flares during Phase 3. Seven rheumatologists on our Planning Committee, selected for their expertise in gouty arthritis and clinical trial design, chose  $B = 8\%$ .

#### Formal statement of the primary hypothesis

$H_0$ : Allopurinol is inferior to febuxostat. The Phase 3 proportion of one or more gout flare events among Allopurinol participants is more than the Phase 3 proportion of one or more gout flare events among Febuxostat participants by 8% or more ( $D \geq 8\%$ ).

[figure not shown]
$H_a$ : Allopurinol is non-inferior to febuxostat. The Phase 3 proportion of one or more gout flare events among Allopurinol participants is not more than the Phase 3 proportion of one or more gout flare events among Febuxostat participants by 8% or more ( $D < 8\%$ ).

The estimate of  $D$ ,  $\hat{D}$ , is the observed treatment difference. The difference is defined so that it is positive when febuxostat has the higher success rate (lower gout flare proportion). To test the null hypothesis, we will compute the upper limit of a one-sided 95% confidence interval for  $D$ :

[figure not shown]
$$U = \hat{D} + 1.645 * \text{stderr}(\hat{D}).$$

The graphic below displays the decision process. In **Figure 1** the upper limit ( $U$ ) is less than  $B$ , and we reject the null hypothesis of non-inferiority; allopurinol is non-inferior to febuxostat. In **Figure 2**,  $U$  exceeds  $B$  indicating that the true difference may be larger than the posited value of  $D$ ; we cannot reject the null hypothesis that allopurinol is inferior to febuxostat.

**Figure 1:** One-Sided 95% Confidence Interval for the Non-inferiority Test Depicting 'Rejection' of the Null Hypothesis

**Figure 2:** One-Sided 95% Confidence Interval for the Non-inferiority Test Depicting 'Acceptance' of the Null Hypothesis

SAS 9.4 will be used to carry out the analysis. Analytic reports will provide the proportions, the differences among proportions, and the upper limit of a one-sided 95% confidence interval, the bound, followed by a report of the results.

#### 5.4.1. Sensitivity Analysis

- (1) The primary analysis will be repeated on the "per-Protocol" sample with adherence as defined in 3.4 to evaluate efficacy among those adherent to the protocol. We will compare the primary results with the analogous results for the per-protocol participants.
- (2) On the "Primary Analysis" cohort assuming all allopurinol patients with missing primary outcome had at least one gout flare during phase 3 of our study while none of febuxostat patients with missing primary outcome had any gout flare during phase 3 (the worst-case scenario).
- (3) On the "Primary Analysis" cohort assuming all febuxostat patients with missing primary outcome had at least one gout flare during phase 3 of our study while none of allopurinol

patients with missing primary outcome had any gout flare during phase 3 (the best case scenario).

## 5.5. Secondary Analysis

All secondary analyses are descriptive exploratory analyses and will be done with and without covariate adjustment (age, sex, disease severity, comorbidities, etc.). In some secondary analyses, we will impute values to explicitly explore the effect of missing data.

We describe the proposed analysis for each of the eight secondary objectives:

- 1) To compare the efficacy and tolerability of allopurinol and febuxostat in hyperuricemic participants with gout and stage 3 chronic kidney disease (CKD 3) in reducing gout flares.
  - a. We will carry out the analogues non-inferiority analysis proposed for the primary objective but restricted to participants with stage 3 CKD, using only gout flares observed during Phase 3. Using the full cohort, we will compare gout flare rates of participants with stage 3 CKD to participants with an eGFR  $\geq 60$  mL/min/1.73m^2 with a logistic regression model.
  - b. Tolerability of the two treatments will also be compared in this patient subset and will include comparisons of proportions of adverse events, serious adverse events, and related study withdrawal during the whole study using logistic regression.
  
- 2) To explore the efficacy of the two ULT dosing regimens in achieving the goal of sUA < 6.0 mg/dl evaluated at the end of phase 2. Besides treatment, the primary predictors include the series of sUA measures and dose titrations prior to 48 weeks. This longitudinal analysis will model deviations from the titration protocol.
  - a. The analysis for these longitudinal data will be the mixed effects model with a variance-covariance structure that assumes auto correlated AR(1) sUA measurements over time. We will use PROC MIXED in SAS. At each clinical visit a binary factor will indicate if the titration protocol is or is not maintained. Besides baseline factors such as age, sex, and duration of disease, the model will incorporate time-dependent factors including side effects. Missing data methods will address potential censoring of events among patients who fail to attend clinic visits.
  - b. We will run the same analysis using the biological threshold of sUA < 6.8 mg/dl at the end of phase 2.

- 3) To determine if there are gout flares in phase 3 in participants who achieve a sUA < 6.0 mg/dl by 48 weeks differ compared to those who do not, regardless of treatment assignment.

The binary outcome for this logistic regression analysis will be the presence of gout flares in phase 3. The analysis will use gout flares in phase 1 and phase 2 as baseline covariates.

- 4) To determine whether health-related quality of life measures differ between participants randomized to allopurinol compared to febuxostat and differ by achievement of sUA < 6.0 mg/dL, regardless of treatment assignment.

- a. EQ-5D-3L & VR-12 instruments will be administered at baseline, 24, 48, and 72 weeks. At each time we will compare the mean scores by treatment groups, using both an unadjusted t-test and linear regression with adjustment for baseline covariates.

- b. With outcome change from baseline to later weeks, we will compare mean changes by treatment group with and without covariates using linear regression.

- c. We will carry out a repeated measures analysis using all time points. Missing data methods will address potential censoring of events among patients who fail to complete the instrument at a particular time.

- d. Analogous analyses will be carried out controlling for sUA levels.

- 5) To determine whether change in tophi area differ by location between participants randomized to allopurinol compared to febuxostat and differ by achievement of sUA < 6.0 mg/dL, regardless of treatment assignment.

- a. Tophi area will be assessed at baseline, 24, 48, and 72 weeks. At each time point we will compare the mean areas by location by treatment groups, using an unadjusted t-test and linear regression with adjustment for baseline covariates.

- b. With area change from baseline to later weeks, we will compare mean changes by location with and without covariates using linear regression.

- c. We will carry out a repeated measures analysis using all time points. Missing data methods will address potential censoring of events among patients who fail to complete the instrument at a particular time.

- d. Analogous analyses will be carried out controlling for sUA levels.

- 6) To determine whether the number of gout flares during all three phases differ between participants randomized to allopurinol compared to febuxostat and then extend this analysis to the entire 72-week period.
  - a. We will model the number of gout flares, which can have substantial variation, as Poisson random variables. We will use Poisson regression to compare treatments using a longitudinal repeated measure (PROC GLIMMIX and GENMOD in SAS). Missing data methods will address potential censoring of events among patients who appear to fail to report flares.
  - b. Flare counts will be analyzed separately during Phases 1, 2, and 3 because dose titration during Phase 1 tends to increase the counts, and this effect may still persist in Phase 2, particularly for those still undergoing dose titration; participants are expected to be in steady-state by Phase 3.
  - c. Phase 2 analysis will consider prophylactic treatment after a gout flare and severe side effects of treatment as predictors of subsequent counts.
  - d. During Phase 3 the same set of factors as well as Phase 2 counts will be used to predict gout flare counts. These time-dependent associations will require a mixed effects model using an auto correlated AR(1) variance-covariance to model the series of events.
  - e. For these analyses we may treat the counts as continuous measures in order to introduce more subtle variance-covariance structure and a variety of random effects.
- 7) To determine the patterns of tolerability/toxicity for each treatment during Phase 3 and then overall from weeks 1-72.
  - a. Toxicity events include rises in sUA levels, adverse changes in serum creatinine, CBC, liver function tests (LFTs), blood pressure, and the incidence of skin rashes. The incidence of cardiovascular events of interest will also be included in this analysis.
  - b. Within each Phase we will determine if the incidence of such events differs between treatments. In the Phase 3 analysis baseline covariates will include the summary of toxicity events during Phases 1 and 2 as well as the week 48 sUA level. As in the sixth secondary analysis the same statistical methods for Poisson counts will be used.
  - c. At each clinic visit we will assess the count of each type of major side effect episodes between visits. The analyses will compare treatments using a longitudinal repeated measures analysis with Poisson count, negative binomial counts, and binary outcomes

(PROC GLIMMAX and GENMOD in SAS). Missing data methods will address potential censoring of events among patients who fail to attend clinic visits.

- 8) To describe the effects of baseline covariates and time-dependent covariates on the primary results.
  - a. We will carry out logistic regression analyses adjusting for covariates and use GEE model.
  - b. Baseline data include demographic characteristics (e.g. age, sex), disease history including CKD level, presence of tophi at baseline, height, weight, laboratory values, medications, other comorbidities, and quality-of-life measures.
  - c. Time-dependent variables include data obtained after baseline include sUA measures, titration levels, and side effects.
  - d. All data obtained before Phase 3 may be used as baseline factors for Phase 3 analyses.

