A strategy of dose titration for each treatment will be employed to bring as many participants as possible below the threshold of sUA < 6.0 mg/dl, established by guidelines and recommendations (7). The Phase 1 titration is intended to bring sUA < 6.0 mg/dl within 24 weeks. All participants will be analyzed during Phase 3 regardless of whether their sUA is < 6.0 or \geq 6.0 mg/dl. We expect that roughly equal numbers of participants in each study arm will reach this threshold. We expect that 75% - 80% participants will have a mean sUA < 6.0 mg/dl across the last 3 study visits occurring during Phase 2 at 36, 42, and 48 weeks. For secondary analysis, we define the binary outcome, mean sUA < 6.0 mg/dl as a treatment success and mean sUA \geq 6.0 mg/dl, as a treatment failure.

Choice of a Bound, B, for the Non-inferiority Test

Non-inferiority tests require expert choice of a bound, B, larger than the true difference, D, between the treatment proportions of participants with flare events (the proportion for febuxostat minus the proportion for allopurinol). The bound marks where clinicians might begin to doubt that the difference, D, is very small and close to zero. Seven rheumatologists on our Planning Committee, selected for their expertise in gouty arthritis and clinical trial design, chose B = 8%.

The null hypothesis will be rejected if U, the upper limit on the one-sided 95% confidence interval on the difference between the two flare-event rates (D), is less than B = 8%. (See Figure 1) If U exceeds B then this indicates that the true difference may be large and that allopurinol is inferior to febuxostat. (See Figure 2)

It is important to note that our choice of a bound is more conservative when compared to many other recent studies. Previous studies have chosen the true bound to be 10% and a true difference in the proportions to be 0% (11). For the non-inferiority test, this more conservative estimate requires CSP 594 to enroll a larger sample size.

Primary Data Analysis Plan

The primary hypothesis to be tested is that allopurinol is non-inferior to febuxostat. The primary outcome is the difference (D) in proportion of patients with one or more gout flares during Phase 3. The proposed test is a one-sided non-inferiority test of the null hypothesis that $U > B$, which the upper limit on the 95% confidence interval on the difference between two proportions exceeds 8%. We posit a true difference in proportions of 0%.

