† sUA drawn at weeks 9, 15, and 21 **only** if prior sUA level not at target threshold (target threshold is defined as sUA < 6.0 mg/dl or < 5.0 mg/dl for tophi);

XII. Potential Pitfalls of the Proposed Study Design and Strategies to Address Them

A major concern of the Planning Committee on the initial submission was for the proposed open-label design. Randomized, double-blind, placebo-controlled trials are regarded as the “gold standard” study design to evaluate efficacy, therefore we have switched to this design. The development of skin rash could “break the blind” if it occurred more commonly in one group, however skin rash has been reported with similar frequency with both of our ULT agents in other blinded trials. To minimize unnecessary withdrawal for all skin rashes, the protocol requires investigators to evaluate all rashes and provides guidelines for study drug discontinuation. Investigators will receive extensive training regarding these guidelines. Specific reporting forms for rash will help document all rashes.

Although we will include patients with stage 3 CKD (eGFR 30-59 mL/min/1.73 m²), we will exclude patients with more severe kidney disease. While stage 3 CKD comprises 7.6% of the most recent NHANES cohort (corresponding to more than 23 million US adults) and more than 10.3% of the VA population, patients with stage 4 CKD comprise less than 0.4% of the US population and less than 0.7% of VA patients (46). Thus, the ability to recruit a sufficient number of patients with advanced CKD and gout to provide a meaningful analysis in this subpopulation is doubtful. In addition, pharmacokinetic studies of febuxostat demonstrate increased concentrations of both parent drug and active drug in patients with severe renal impairment (creatinine clearance <30 mL/min) and there are insufficient data regarding drug dosage and safety in this population (104). Dose reduction of allopurinol is also recommended in patients with severe renal impairment (105), which may necessitate an adjusted dose titration if patients with more severe CKD were included in the study. Moreover, both NSAID and colchicine prophylaxis are contraindicated in patients with more severe CKD (stages 4 or 5), which may skew results in that subset of patients. For these reasons we will have targeted recruitment to include patients with stage 3 CKD but will exclude patients with more severe degrees of renal impairment at study enrollment.

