## 2. Overview of the Study Design and Objectives

The proposed study is a double-blinded, two-arm intervention trial testing whether appropriately titrated allopurinol is non-inferior to appropriately titrated febuxostat.

Participants will be recruited from 19 Veteran Affairs and 5 RAIN sites. Individuals with a history of gout who continue to be hyperuricemic (sUA  $\geq$  6.8mg/dl) and fulfill entry criteria will be invited to participate. A total of 950 participants will be randomized in a 1:1 ratio to receive either allopurinol or febuxostat. Recruitment will occur over 24 months. The total duration of the trial will be 4 years.

Participants will be followed for 72 weeks: a 24-week Dose Titration Phase (Phase 1) followed by a 24-week Maintenance and Optimization Phase (Phase 2) and then a 24-week Steady State Flare Observation Phase (Phase 3). Patients will undergo active surveillance during Phases 1 and 2 with scheduled in-person study visits, while Phase 3 observation will be conducted remotely using telephone encounters. There will be one study visit at week 60 to return bottles and diaries and pick up a new three-month supply of study medication.

The primary objective:

To compare the efficacy of appropriately titrated doses of two ULTs, allopurinol and febuxostat, in reducing gout flares during Phase 3, weeks 49-72, in participants with gout who are hyperuricemic prior to study entry.

Secondary Objective:

- 1) To compare the efficacy and tolerability of allopurinol and febuxostat in reducing gout flares among participants with gout who have stage 3 chronic kidney disease (CKD 3) and are hyperuricemic at baseline.
- 2) To compare the efficacy of the two ULT dosing regimens in achieving sUA < 6.0 mg/dL between weeks 36 and 48 (i.e., during Phases 1 and 2: the dose titration phase, and the dose maintenance and optimization phase).
- 3) To determine if the number of gout flares in phase 3 in participants who achieve a sUA < 6.0 mg/dl by 48 weeks differ compared with those who do not, regardless of treatment assignment.
- 4) To determine whether health-related quality of life measures differ between participants randomized to allopurinol compared to febuxostat and differ by achievement of sUA < 6.0 mg/dL, regardless of treatment assignment.

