#### **3.5.2. Secondary outcomes**

The secondary outcomes will include:

- 1) The efficacy and tolerability in patients with CKD 3.
  - i. To determine whether the efficacy of allopurinol and febuxostat differ among those with Stage 3 CKD, a planned secondary endpoint will be the occurrence of gout flares during Phase 3 in this patient subset.

- ii. Tolerability of the two treatments will also be compared in this patient subset and will include comparisons of adverse events, serious adverse events, and related study withdrawal.
- 2) The proportion of patients achieving a sUA < 6.0 mg/dl during Phase 2 (mean level assessed at weeks 36, 42, and 48) across treatment groups.
  - 3) The proportion of having at least one gout flares in Phase 3 differ in those who reach a target sUA of < 6.0 mg/dl compared with those who do not by 48 weeks.
  - 4) The impact of study treatments and sUA levels on health-related quality of life.

Both the five-item EurQol (EQ-5D-3L) and Veterans RAND 12 (VR-12) will be collected from all participants at baseline, 24, 48 and 72 weeks.

- 5) The changes in tophi area by location among those with tophaceous gout across treatment groups and sUA levels.

We anticipate that ~20% of study participants will have tophi at enrollment. The sentinel tophus will be defined as the most prominent and/or most readily measured tophus found at the time of the baseline evaluation on the hands, elbows, feet, or ears (i.e., the most common sites for tophi). Change in tophi area will be examined at week 24, week 48, and week 72 as a secondary outcome among this informative subset of patients with tophaceous gout.

- 6) The impact of treatment on the flare rate over time.

To determine whether the total number of gout flares differs between the two treatment groups the total flare numbers occurring during observation (week 0 to 72) will be compared.

Recognizing that the duration of a gout flare typically extends from several days to 2-3 weeks, and that it may sometimes be difficult for patients to distinguish between two or more back-to-back flares and one persistent but fluctuating flare, a maximum of one gout flare will be counted for each one-month observation period. Thus, as an example, during Phase 3 (24 weeks) patients could experience a number of gout flares ranging from 0 to 6 flares.

- 7) The tolerability/toxicity of the two ULTs.

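### Secondary objective 2 is defined as a proportion at the sUA target, but the mixed model assigned to it does not give the between-arm difference in that proportion

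*SAP*

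**What the plan says.** - **Endpoint.** SAP 3.5.2, outcome 2, is "The proportion of patients achieving a sUA < 6.0 mg/dl during Phase 2 (mean level assessed at weeks 36, 42, and 48"), compared across treatment groups. Protocol Section VIII (Estimated Incidence of the Primary Endpoint) uses the same three visits and says "we define the binary outcome, mean sUA < 6.0 mg/dl as a treatment success", with anything else a failure. Protocol Section VII places it among the key secondary outcomes.
- **Timing.** SAP Section 2 words the objective as efficacy "in achieving sUA < 6.0 mg/dL between weeks 36 and 48". SAP 5.5 words it as efficacy "in achieving the goal of sUA < 6.0 mg/dl evaluated at the end of phase 2".
- **Analysis.** SAP 5.5 objective 2 specifies a mixed effects model with a "variance-covariance structure that assumes auto correlated AR(1) sUA measurements over time" and adds "We will use PROC MIXED in SAS". Apart from treatment, the main predictors are the run of sUA values and the dose changes before week 48. A per-visit flag for keeping to the titration protocol, baseline factors and time-dependent factors such as side effects are also included. The response is not named. Item b then says "We will run the same analysis using the biological threshold of sUA < 6.8 mg/dl at the end of phase 2". Protocol Section VIII (Secondary Data Analysis, objective 2) gives essentially the same text.
- **Draw schedule.** Under Protocol Section XI and Table 5, everyone has sUA drawn at weeks 0, 6, 12, 18, 24, 30, 36, 42 and 48. Draws at weeks 9, 15 and 21 are made only "if prior sUA level not at target threshold".
- **Status.** SAP 5.5 classes all secondary analyses as descriptive and exploratory.

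**The concern.** The endpoint is one yes/no value per patient, summarised as a proportion in each arm. The analysis is a longitudinal model in a procedure for Gaussian responses. Nothing in SAP 5.5 says how the model leads to the two proportions, their difference or a confidence interval. The same section names logistic regression for the binary questions in objectives 1 and 3, and GLIMMIX/GENMOD for the binary outcomes in objective 7, so objective 2 stands out.

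This outcome shows whether titrated allopurinol brings patients to target as often as titrated febuxostat. If the text stays as it is, the response, the time point and the method for that comparison can all be settled after the data are seen. A published estimate could then be a mean difference, or a treatment effect adjusted for the very sUA values and doses through which treatment acts, and neither is the quantity that the plan defines.

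**Working it through.** The documents state no sample size, power or precision for objective 2, so there is no figure of the plan's own to reproduce. The check is to take each possible response and ask what the written model returns.

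1. **Continuous sUA at each visit.** The treatment term is a contrast in mg/dl. No threshold enters the model, so the 6.8 rerun is the same model with the same output.
2. **One 0/1 indicator per patient (mean of weeks 36, 42 and 48 below 6.0).** There is one response per patient, so AR(1) has no repeated measurements to describe. The sUA values before week 48 are named predictors, and these include weeks 36 and 42, two of the three values that form the endpoint. The treatment coefficient is then conditional on most of the outcome and on post-randomisation dose.
3. **A 0/1 status at each visit.** PROC MIXED has no link function for a binary response. Visit-by-visit status is not the three-visit mean, and the post-randomisation predictors remain.

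None of the three gives the arm difference in the defined proportion.

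**Can a mean contrast stand in for the proportion?** Assume normal sUA with common SD s (not in the documents; range 0.8 to 2.0 mg/dl) and 77.5% at target in one arm, the midpoint of the Protocol's expected 75% to 80%. Then (6.0 − mean)/s = 0.755. Raising the mean by an illustrative 0.3 mg/dl gives a proportion of Φ(0.755 − 0.3/s).

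| s (mg/dl) | Proportion below 6.0 after the shift | Difference from 77.5% |
|---|---|---|
| 0.8 | 64.8% | 12.7 points |
| 1.0 | 67.6% | 9.9 points |
| 1.5 | 71.1% | 6.4 points |
| 2.0 | 72.8% | 4.7 points |

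One mg/dl difference is compatible with nearly a threefold range on the endpoint's scale.

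**Precision of the direct comparison.** The half-width is 1.96 × √(2p(1 − p)/n), with n = 425 per arm from SAP Section 4. That number is set for the primary analysis; the number evaluable for objective 2 is not given.

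- p = 0.75: 1.96 × √(0.375/425) = 5.8 points
- p = 0.775: 1.96 × √(0.34875/425) = 5.6 points
- p = 0.80: 1.96 × √(0.32/425) = 5.4 points

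**Side check on AR(1).** A participant at target from week 6 has 9 draws, all 6 weeks apart. One never at target has 12 draws, with gaps of 6, 3, 3, 3, 3, 3, 3, 6, 6, 6 and 6 weeks. If records were indexed in draw order, one lag correlation would cover both gaps. With an assumed 6-week correlation of 0.5, the time-consistent 3-week value is √0.5 = 0.71; for 0.3 to 0.9 it is 0.55 to 0.95. Weeks 36, 42 and 48 are nominally evenly spaced.

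**The case against.** Four arguments favour leaving the plan alone.

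- **The proportion appears elsewhere.** SAP 5.3 tabulates categorical variables by arm with chi-square tests. Protocol Section VIII applies chi-square or Fisher tests to selected variables, including laboratory and alternative outcomes. SAP Tables C1 and C2 count subjects with mean sUA below 6.0 and 6.8. A reader might infer that the endpoint is estimated nowhere, and these provisions show that this goes too far. They still do not fill the gap: the SAP 5.3 tests are there to check balance, the Protocol does not say that this outcome is among its selected variables, and the table shells have a single column with no arms. None gives a difference with a confidence interval for objective 2.
- **The response may be thresholded.** The 6.8 rerun suggests so, and a 0/1 response in a linear model with treatment alone would give a difference in proportions. It is right that the documents never say that the response is continuous sUA. But that simple model is not the one written. The with-and-without-adjustment clause in SAP 5.5 lists age, sex, severity and comorbidities; it does not say that the sUA series and titrations, named as main predictors, would be dropped.
- **Spacing is minor.** This stands. The common schedule is 6-weekly, only the conditional draws and the visit windows break it, and the SAP does not say which draws enter the model or how they are indexed. Spacing is not why the proportion is missed.
- **It is exploratory.** This also stands, and it limits the severity. It does not make a mismatched analysis fit its endpoint.

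**Conclusion.** The point holds for the assigned analysis. SAP 5.5 objective 2, as written, does not yield the between-arm difference in the proportion with mean sUA below 6.0 mg/dl over weeks 36, 42 and 48, whichever response is assumed. This follows from the text and needs no numerical assumption. The conversion from mean to proportion rests on assumed normality and SD, and serves only to show that a mg/dl contrast is no substitute. The 5.6-point half-width describes the replacement analysis; it does not measure harm from the present one.

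Two stronger readings are not supported. A reader might infer that AR(1) makes the standard errors for this endpoint wrong, but no such error can be sized from the documents and the three defining visits are nominally evenly spaced. A reader might also infer that the trial's main result is at risk. It is not: objective 2 has no alpha, power or margin, and the Phase 3 flare comparison does not use this model. The change should be made, but nothing in the primary analysis depends on it.

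**What to change.** In SAP 5.5 objective 2:

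1. Name the response: an indicator that mean sUA over weeks 36, 42 and 48 is below 6.0 mg/dl, repeated at below 6.8. State how the mean is formed when one or more of the three values is missing.
2. Compare arms by a difference in proportions with a 95% CI, or by logistic regression with treatment and the baseline randomisation factors only. Leave post-randomisation sUA and dose out of this model.
3. Reconcile the timing, so that Section 2, Section 3.5.2 and Section 5.5 all refer either to weeks 36 to 48 or to one stated meaning of the end of Phase 2.
4. Keep the mixed model as a supportive analysis, with continuous sUA named as its response. If the week 9, 15 and 21 draws enter it, index the correlation by actual time (for example spatial power), or restrict the model to the common 6-weekly visits.

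The cost is a few lines of SAP wording and a small amount of programming. No new data are needed, because all the sUA values are already scheduled.
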